Official title: Treatment of unfavorable bleeding patterns in contraceptive implant users: a randomized clinical trial of curcumin

> Principal Investigator: [name], MPH

> > NCT No: 04205929

Protocol Version Date: October 15, 2019

- 1 Title: Treatment of unfavorable bleeding patterns in contraceptive implant users: a randomized
- 2 clinical trial of curcumin
- 3
- 4 PI: [name], MPH
- 5 Oregon Health & Science University
- 6 [name]
- 7 [name]
- 8 [contact]
- 9 [contact]
- 10
- 11 **Co-I:** [name], MPH
- 12 [name], FNP
- 13 [name], FNP
- 14
- 15 **Funder:** Investigator initiated
- 16

17 Background:

The etonogestrel (ENG) subdermal contraceptive implant (ENG implant) is a highly effective 18 method of preventing pregnancy, but it has bleeding side effects that make it unappealing for 19 20 many women. Given that the ENG implant is 20 times more effective at pregnancy prevention than oral contraceptive pills, strategies to increase its acceptability will translate into improved 21 22 prevention of unplanned pregnancies [1]. Many medications have been studied with progestin-23 only contraceptives such as the ENG implant to manage irregular bleeding. Concurrent use of oral contraceptives (OCs) with the implant does stop bleeding but bleeding returns when OCs 24 25 are stopped [2, 3]. The only study to demonstrate a sustained reduction in bleeding lasting for two months was the selective estrogen receptor modulator (SERM) tamoxifen in users of the 26 levonogestrel (LNG) contraceptive implant [4]. We conducted a small clinical trial to evaluate 27 the effects of a 7-day course of tamoxifen in users of Nexplanon[®] with bothersome 28 breakthrough bleeding, and demonstrated that tamoxifen treatment reduces bleeding/spotting 29 days during the first 30 days after use as compared to placebo [5]. Recently, we successfully 30 31 completed a study that expanded on our original tamoxifen work and found similar results over a 32 90-day time period (Merck IIS, paper under development). 33

34 We have proven that tamoxifen is a successful strategy to stop breakthrough bleeding in implant 35 users but providers and patients do have concerns about this particular drug since it is used for 36 cancer. Tamoxifen also has a small increased risk of venous thromboembolism (VTE) with 37 continuous use in a menopausal population. Healthly reproductive-age woman with short-term exposure to tamoxifen have not been shown to have a risk of VTE but the concern is still 38 present as well as the stigma that it is a 'cancer' drug. If another agent without these concerns 39 could be found to improve bleeding in implant users then this drug might be more widely 40 41 adopted.

42

The exact mechanism of progestin-induced bleeding is unknown but it is likely multi-factorial with the end result of angiogenesis, 'leaky' fragile vasculature, and inflammation. Curcumin, the

45 active ingredient in turmeric, has been demonstrated to be anti-inflammatory, anti-proliferative,

46 and anti-angiogenic which may make it an ideal agent for the management of break-through

- bleeding. The FDA has determined curcumin is safe and categorizes it as 'generally regarded
- 48 as safe' (GRAS). Studies have demonstrated that curcumin is extremely well-tolerated.
- 49 Curcumin has a significant body of evidence as an adjunct treatment in patients with cancer,
- 50 cardiovascular disease and auto-immune/inflammatory conditions. In terms of women's health,
- 51 curcumin was better than placebo in a randomized control trial in attenuating the severity of

52 PMS symptoms but has not been studied for uterine bleeding. Anecdotally, naturopaths and 53 herbalists use it for treatment of heavy menstrual bleeding.

53 54

69

71

72

79

83 84

85

86

87

88 89

90

91

 2007.
- 58 [2] Guiahi M, McBride M, Sheeder J, Teal S. Short-term treatment of bothersome bleeding 59 for etonogestrel implant users using a 14-day oral contraceptive pill regimen: a 60 randomized controlled trial. Obstet Gynecol 2015; 126: 508-13
- [3] Hou MY, McNicholas, C, Creinin MD. Combined oral contraceptive treatment for
 bleeding complaints with the etonorgestrel contraceptive implant: a randomized
 controlled trial. Eur J Contracept Reprod Health Care 2016; 21:361-6.

105 first dose will be taken at the start of enrollment if the subject is on the 3rd day of active bleeding 106 or if not bleeding, on day 3 of the next bleeding episode. The study will be conducted at Oregon Health & Science University (OHSU) in Portland, Oregon 107 108 Each subject's involvement will be up to approximately 60 days as study drug will not be 109 initiated at the time of enrollment unless they are experiencing bleeding/spotting that day and 110 the two prior days to enrollment. Study drug will be started on the 3rd day of an active bleeding 111 episode. If no active bleeding episodes happen in the first 30 days from enrollment then the 112 participant will be withdrawn from the study. The study will require up to 3 in-person study visits 113 [screening (V1), enrollment (V2), and a close out visit or study exit (V3)], as well as a daily 114 response to a text or email message about bleeding and use of study medication. Additional 115 116 phone and email contact may occur with the participant to ensure clarity of diary entry or completion or to ensure drug initiation and compliance. The electronic diary only takes a few 117 118 seconds to complete ...

119

Eligibility: 120

- 121 Inclusion:
- 122

125 126

134

136

137

- English speaking women 15-45 years of age currently using the ENG implant who have experienced frequent or prolonged bleeding while using the device: 123 124
 - To be eligible, women will need to have >7 days of continuous bleeding/spotting 0 in the last 30 days, OR 2 or more episodes of bleeding/spotting in the last 30 davs.
- 127 Implant use for at least 30 days prior to screening visit.
- 128 Willing to continue using the implant for at least 30 days from study enrollment.
- Access to a reliable cell phone and must be willing to receive and respond to a daily text 129 or email message to assess bleeding and use of study drug 130
- Implant must be palpable to prove that an ENG implant is in place at time of screening 131 132 and enrollment. 133
 - Negative gonorrhea/chlamydia screening performed at screening visit •

135 Exclusion criteria:

- Postpartum within six months •
- Post-abortion within six weeks •
- Currently pregnant 138 •
- Currently breast-feeding (to be eligible, must be 4-6 weeks from cessation of 139 140 breastfeeding)
- Undiagnosed abnormal uterine bleeding pre-dating placement of contraceptive implant 141 •
- 142 Bleeding dyscrasia •
- Anticoagulation use 143 •
- Active cervicitis 144 •
- 145 Allergy to curcumin or turmeric •
- History of venous thromboembolism 146 •
- Current or past breast or uterine malignancy 147
- Use of P450 pathway inducing drug 148
- Implant is due to be switched out in 2 months or less from enrollment 149 •
- Currently using oral contraceptives in addition to implant (to be eligible, needs to have a • 150 4-6 week washout period) 151

152

Prior pregnancy occurred while Nexplanon/Implanon was in place

153

154 Study procedures155

156 Screening (Visit 1, V1). Estimated 1 hour

Eligibility and study consent will be signed at this visit. Baseline demographic information will be collected by interview, including menstrual history, contraception history including timing of implant placement, sexual and pregnancy history, BMI/weight, ethnicity, age, and baseline use of panty liners (as advised by Mishell et al 2007 to avoid confounding data on bleeding/spotting days). A series of questions will be asked to quantify number of bleeding and spotting days and frequency and duration of bleeding episodes over the preceding three months of implant use (or since placement, if less than three months). Current implant use will be confirmed via palpation.

164

165 Physical exam including blood pressure check, pelvic examination, urine pregnancy test,

- 166 cervical cytology evaluation (if not completed within the ASCCP recommended screening
 167 interval), and testing for gonorrhea and chlamydia. A baseline assessment of satisfaction with
 168 baseline bleeding pattern will also be performed.
- 169
- 170 Once negative results from the subject's gonorrhea and chlamydia testing are demonstrated,
- 171 visit 2 can be scheduled (enrollment).
- 172

173 Enrollment (V2), estimated 30 minutes

This visit could be combined with the screening visit. Randomization for part 1 of the study will occur at this visit. Pregnancy test and blood pressure will be performed. The Subject Study Drug

- 176 Information Handout will be provided and explained. Study drug will be provided. Subject will
- 177 only start study drug at this visit if they are experiencing an active bleeding episode and this is
- the 3rd day of bleeding/spotting. Study coordinator will instruct how to start tracking bleeding via
- text message. Subjects will receive training on the use of the electronic bleeding diary
- 180 procedures. This includes instruction on use of the text or email message bleeding diary.
- 181
- 182 End of study (V3), estimated 30 minutes

183 The final visit will take place approximately 90 days after enrollment or at the time of study

- 184 withdrawal/exit. Repeat STI testing only if indicated by a change in partners during the study.
- 185 Vital signs will be performed and a review of bleeding diary, medications, AEs, and health
- 186 changes. A short satisfaction questionnaire will be performed. Participation is complete after
- this visit. Unused study drug will be retuned at these visits.
- 188

Details
 Informed consent Review medications Confirm implant use Physical exam with vitals (blood pressure, pulse, weight, height) Urine pregnancy test Review eligibility criteria Gonorrhea and chlamydia test Pap (if indicated) Basolino questionnaire

Visit 2– enrollment	 Review bleeding diary with staff Review medications Vitals (blood pressure, pulse, weight, height) Confirm implant use Receive placebo or study drug and instructions Review any health changes
Visit 3- end of study	 Urine pregnancy test if indicated Repeat Gonorrhea and chlamydia test if change in partner occurs during study. Review medications Return any unused medication Vitals (blood pressure, pulse, weight, height) Confirm implant use Review bleeding diary with staff Review health changes Exit guestionnaire

189

190 Description of intervention/study drug

191 Participants will be instructed to begin use of the study medication daily. A study coordinator

192 (SC) will prospectively follow electronic bleeding diaries at a minimum of three times weekly for

193 each individual study subject to ensure data integrity and correct day of drug initiation. Any

unused study drug will be counted and returned at the conclusion of the study.

195

Failure to complete the texting diary will prompt a phone call or email from the SC. If we are unable to reach a subject by phone, email, letter over a 2-week time period, their participation will be terminated. Any data obtained up to this point will be analyzed in accordance to with

intention to treat.

200

201 Study procedures and data collection other than side effects and AEs will last 30-days from 202 enrollment.

203

204 Compensation

Participants will be compensated up to \$250 for their participation in this study. Study visit compensation breakdown is as follows:

- 207
 Visit 1- Screening:
 \$50

 208
 Visit 2- Enrollment:
 \$50

 209
 Visit 3- Study end
 \$50

 210
 Diary Completion:
 \$100
- 211

212 Subjects will only be compensated for the visits they complete. For example, if a subject

withdraws after visit 2, they will only be compensated for those two visits (\$50 + \$50).

214 Diary compensation

215 Diary completion is defined as responding to 1 daily text message per day. A subject can miss

- up to 2 days of responses in the up to 60-day study period and still receive diary compensation.
- 217 If a subject misses 3 or more days of diary entry in a given 30 days, they will not receive this

- compensation. Study coordinators will be tracking diary responses, and response rates. If a
- subject withdraws early from the study, they will only receive compensation for visits that they have completed and not the compensation for diary completion.
- 221

222223 Sample size

224 Our primary outcome is the total number of amenorrhea days in a 30-day reference between 225 curcumin and placebo groups. Our prior tamoxifen study demonstrated a 6-day difference in 226 overall amenorrhea days in the first 30-day reference period.

227

Based on our recent tamoxifen study, a sample size of 44 women allows us to demonstrate a 6day difference between groups; 80% power at an alpha 0.05 = 22 women per each group. To
account for drop out, we have increased the sample size by approximately 30% for a total
sample size of 58.

231 232

233 Study drug

- 234 Curcumin an active ingredient in the spice Tumeric is a natural polyphenol. It is purported to
- have multiple health benefits mostly based in its anti-inflammatory and anti-oxidant properties.
- 236 Curcumin dosing has been demonstrated to be well tolerated in humans up to 12,000mg/day
- but dosing as a cancer treatment adjunct or as an autoimmune therapy are in the 400-
- 600mg/day range [1,2]. In general, subjects seem to experience no side effects from curcumin
- but in a dose escalation study to determine safety and tolerability, 7 of 34 subjects experienced
- 240 headache, rash, and yellow stool. At higher doses, some nausea and diarrhea have also been
- 241 reported. Curcumin may have a beneficial effect on cholesterol and triglycerides. Curcumin has
- 242 poor bioavailability and combining it with piperine, a known bioenhancer derived from black
- 243 pepper, has been shown to improve curcumin bioavailability by 2000% [3]. However, curcumin
- without a bioenhancer has also demonstrated therapeutic impact in randomized controlled trials.
- 245 We plan to use Theracurcumin by Immunovites, 600 mg curcumin, as they report quality testing
- and have combined curcumin with a bioenhancer for improved bioavailability. This product also
- 247 contains ginger root powder and bioperine (derived from black pepper).
- 248 (https://immunovites.com/products/theracurmin-hp-max).
- 249 Curcumin is considered a supplement by the US Food and Drug Administration. The FDA has
- 250 determined curcumin is safe and categorizes it as 'generally regarded as safe' (GRAS). Our
- IRB chair has recommended that we seek the FDA's opinion regarding the need for an IND for
- this study as curcumin is a supplement. However, this study is not intended to support a
- significant change in advertising for curcumin. It is also debatable whether its use is for
- 254 "treatment" of a disorder or a study of the impact of curcumin on biological function.
- [1] Esmaily, H.; Sahebkar, A.; Iranshahi, M.; Ganjali, S.; Mohammadi, A.; Ferns, G.; Ghayour-Mobarhan, M. An investigation of the effects of curcumin on anxiety and depression in obese
- Mobarhan, M. An investigation of the effects of curcumin on anxiety and depression individuals: A randomized controlled trial. Chin. J. Integr. Med. 2015, 21, 332–338.
- [3] Shoba, G.; Joy, D.; Joseph, T.; Majeed, M.; Rajendran, R.; Srinivas, P.S. Influence of
- piperine on the pharmacokinetics of curcumin in animals and human volunteers. Planta Med.
- 263 1998, 64, 353–356.
- 264

265 **Risks to Subjects**

- Human Subjects Involvement and Characteristics 266
- 267 Reproductive-aged (15-45 year old), healthy women currently using a contraceptive implant with 268 no contraindications to the study medication and not at risk for or seeking pregnancy will
- constitute the target population for this study. 269 270
- All enrollment and clinical evaluations will be performed at OHSU in Portland, Oregon. 271
- Gonorrhea and chlamydia testing and pap testing (if indicated) will be sent to the OHSU core 272
- 273 lab for routine processing.
- 274
- 275 Sources of Materials
- 276 The sources of research material for the clinical portion of this proposal will be new specimens obtained purely for this research protocol. The study investigators and/or research 277
- 278 assistants/nurses will perform all study procedures.
- 279
- Potential Risks 280
- 281 One risk to taking part in this study is that the study drug may not be effective in helping to treat 282 bleeding.
- 283

The study drug is extremely well tolerated even up to extremely high doses and is considered 284 285 safe by the FDA. At the highest doses, which we are not utilizing here, a few subjects reported 286 nausea and diarrhea.

287

Some parts of the study may be inconvenient including the text messaging to collect data. 288

- These are regular text or email messages and will count towards text messages or data on a 289
- 290 subject's cell phone plan. The subject will be asked detailed questions about her bleeding and
- gynecologic history. Some of these questions may seem very personal or embarrassing. 291
- 292 Women may refuse to answer any of the questions that they do not wish to answer.
- 293

Adequacy of Protection Against Risk 294

Recruitment and Informed Consent 295

- Attempts to enroll a diverse study population will be made through placement of IRB approved 296 297 flyers in the community, community outreach (radio and print ads) and through the availability of
- foreign language interpreters and research staff. Women may also learn of the study through 298
- 299 their routine visits in clinics or by working at OHSU. We also intend to utilize an EPIC Cohort
- 300 search to identify and contact potential participants via phone, email, letter, and/or MyChart
- 301 messages. We intend to use REDCap for batch emailing. We also intend to use Trialspark and 302 Google AdWords as well as Facebook and Instagram for community outreach.
- 303
- 304 Women will be screened for eligibility and if they meet the basic criteria and agree to participate, they will undergo informed written consent. The protocols and consent will be reviewed and
- 305
- 306 approved by the OHSU IRB prior to initiation of the study.
- 307
- 308 Protection Against Risk
- The drug utilized in this study will be used in accordance with dose and routes that the FDA has 309
- 310 determined to be safe. Women will be informed that they will be using a supplement and this is
- not an FDA approved drug but that we have specifically chosen a dose and length of exposure 311
- time to the drug or compound with extremely low potential for significant side effects or serious 312
- 313 risks. Women will undergo screening for any known contraindications to the study drugs.
- 314

- 315 Confidentiality of personal health information will be maintained according to HIPAA
- requirements for research. All subjects will receive a study number to which all subsequent
- data will refer. Personal identifiers will not be on questionnaires, data, abstract sheets, or in the
- main database. All data will be kept in locked files or a password protected computer in the
 Principal Investigator's (PI) office.
- 319 320

321 Data and safety monitoring of plans for clinical trials

The PI and study staffs are responsible for recording the data, and they will be verifying its 322 323 accuracy throughout the process. The PI will be reviewing the data in-depth upon completion of the study. The PI will also be overseeing that the study procedures are being carried out as per 324 the approved protocol via close supervision of study visits and procedures and through frequent 325 communication with the study staff. The PI will also be conducting an initial assessment and 326 periodic assessments of the study and its procedures. If any safety concerns arise, a data 327 328 safety monitoring board will be convened to review the study. As this study will be performed in 329 conjunction with the Women's Health Research Unit's (WHRU), an independent chart audit to ensure data integrity and completeness will be performed after the first 5 subjects have been 330 331 enrolled and then at regular 6 months intervals.

332

333 The PI will adhere to OHSU's Institutional Review Board (IRB) policies regarding protection of

human subjects and the reporting of study deviations and adverse events. In the rare case of an

adverse event, she will utilize the WHRU data safety monitoring board (DSMB) to review the event and rule on a course of action. The WHRU DSMB is made up of individuals

knowledgeable about women's reproductive health and therapies and will have no conflict of

338 interest with the study or its outcomes.

339340 *Data Storage*

341 Data for this project will be stored in OCTRI's installation of REDCap, a highly secure and robust 342 web-based research data collection and management system.

- 343 Features of REDCap that protect participants' privacy and data security include:
- Physical Security: OCTRI's REDCap software is housed on servers located in ITG's
 Advanced Computing Center providing locked physical security
- Belectronic Security: The REDCap servers are housed behind both the OHSU firewall
 and a second ACC firewall. All web-based data transmissions are encrypted with
 industry-standard SSL methods.
- 349oControlled User Access: REDCap is employs a robust multi-level security system that350enables researchers to easily implement "minimum necessary" data access for their
- research staff, including specification of data fields that are identifiers. This feature
 includes "single click" ability to provide completely deidentified (removing all identified
 data fields and shifting dates) for analysis or other purposes. User activities are
 logged to enable auditing of all data access. Access is integrated with OHSU's
 network such that users who are also OHSU employees are authenticated against
- 356 their OHSU network credentials.
- 357 o Data Integrity: REDCap is jointly managed in accordance with OHSU Information
 358 Security Directives by ACC staff and members of OCTRI's Biomedical Informatics

359 Program, ensuring fidelity of database configuration and back-ups. User activities are360 logged to enable auditing of all data changes.

361 Data Sharing

- 362
- 363 We intend to use "Box" to share study documents and spreadsheets.

364 365 Potential Benefits of the Proposed Research to the Subjects and Others

366 There are no direct benefits to study participants.

367368 Importance of Knowledge to be Gained

- 369 This study will increase the knowledge regarding breakthrough bleeding and contraceptive
- implants. It may help to prolong continuation of contraceptive implant use which in turn could
- help women avoid unplanned pregnancies.
- 372

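### Current or recent use of curcumin or turmeric supplements is not excluded, so women already taking the test agent could be randomized and dilute the curcumin-placebo difference

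*Combined protocol and SAP*

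**What the plan says.** In the Eligibility section, curcumin and turmeric appear once, in the exclusion list: "Allergy to curcumin or turmeric". No inclusion or exclusion criterion addresses taking them.

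Three other exclusions concern products a woman may be using: "Anticoagulation use", "Use of P450 pathway inducing drug", and oral contraceptives. The last reads "Currently using oral contraceptives in addition to implant (to be eligible, needs to have a" and goes on to require a washout of 4 to 6 weeks. None of them names curcumin or turmeric.

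Two procedures might pick up existing use. The visit table lists "Review medications" at V1, V2 and V3. Under Protection Against Risk the protocol says "Women will undergo screening for any known contraindications to the study drugs". Neither mentions supplements or says what follows if use is found, and existing use is nowhere called a contraindication.

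On availability, the Study drug section says "Curcumin is considered a supplement by the US Food and Drug Administration". The Background says, explicitly as anecdote, that naturopaths and "herbalists use it for treatment of heavy menstrual bleeding".

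**The concern.** The hypothesis compares daily curcumin with placebo over a 30-day reference period. That contrast is clean only if women in neither arm take curcumin from another source. Staff who applied the criteria exactly as written would randomize a current user. In the placebo arm she could continue her own product. In the curcumin arm the study product would be added to what she already takes, so her gain may be smaller than that of a woman new to it. If curcumin works, both cases shrink the difference. Intention to treat is the only analysis principle the protocol names, and it would keep such women in the comparison. A null result would then be harder to interpret, because lack of effect and contamination could not be told apart.

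The protocol already applies this reasoning to oral contraceptives: the Background says that adding them to the implant stops bleeding, and the exclusion list controls them with a washout. The agent under test has no parallel rule.

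The exposure window is also longer than the treatment period. Randomization takes place at V2, but a woman who is not then on day 3 of a bleeding episode waits for the next one, for up to 30 days. Outside use could begin or continue during that wait.

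**Working it through.** **1. The plan's own figures.** The Sample size section gives a 6-day difference, 80% power, alpha 0.05 and 22 per group (44 in all), raised by about 30% to 58. No SD or sidedness is stated, so the 22 cannot be reproduced independently. Assuming a two-sided two-sample t-test, the SD that makes 22 per arm give 80% power is

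SD = 6 / 0.8646 = 6.94 days,

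where 0.8646 is the standardized difference detectable with 22 per arm. The normal approximation gives 6 × √(22/2) / (1.960 + 0.842) = 7.10 days. The total follows as 44 × 1.3 = 57.2, taken up to 58, or 29 per arm.

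**2. Dilution model (assumption).** Let f be the share of women in each arm already using curcumin or turmeric. The documents do not give f. In the worst case users show no difference between arms, and the expected difference is 6 × (1 − f). Power is that of the two-sided t-test at 0.05 with SD 6.94.

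| f | Women among 58 (58 × f) | Difference, days | Power, 22 per arm | Power, 29 per arm |
|---|---|---|---|---|
| 0% | 0 | 6.00 | 80.0% | 89.9% |
| 2% | about 1 | 5.88 | 78.4% | 88.7% |
| 5% | about 3 | 5.70 | 75.9% | 86.7% |
| 10% | about 6 | 5.40 | 71.3% | 82.9% |
| 20% | about 12 | 4.80 | 61.1% | 73.5% |

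The 22-per-arm column is the plan's evaluable target. The 29-per-arm column applies only if nobody drops out.

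**3. A milder case.** If users lose half of the contrast, the difference is 6 × (1 − f/2). At 22 per arm, f = 5% gives 5.85 days and 78.0% power, and f = 10% gives 5.70 days and 75.9%.

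**4. Size needed to restore 80% (worst case, same t-test).** At f = 5%, 10% and 20%, 25, 27 and 34 evaluable women per arm would be needed in place of 22.

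**The case against.** The case for leaving this alone has several parts.

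- **Use may be rare.** The Background marks the remark about herbalists as anecdotal. It concerns heavy menstrual bleeding, not breakthrough bleeding on an implant. Nothing in the documents says that implant users take curcumin. This stands: f is wholly assumed, and nothing supports the upper values in the table.
- **An ordinary product is not the study product.** The Study drug section describes 600 mg of curcumin with a bioenhancer, calls curcumin poorly bioavailable, and says piperine improves this by 2000%. Zero contrast among users is therefore a worst case. This stands in part: the same section says that curcumin without a bioenhancer has also shown therapeutic effect in randomized trials, so some dilution remains possible.
- **The medication reviews may reveal use.** They may, but no eligibility or analysis rule follows from a positive answer.
- **An instruction may exist elsewhere.** The subject handout on the study drug is not part of this document and the consent text is not available. Either could tell women not to take other curcumin. That would cover the period on study, but it would not fill the gap in the eligibility list.
- **The bias runs only toward no effect.** This is correct under the model used here. It lowers the urgency, but an avoidable loss of sensitivity still matters in a trial of 58.

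A reader might also infer that a current user assigned curcumin has already failed on it, because she qualified by bleeding. The documents do not support that. She may have started the supplement after the qualifying bleeding within the 30-day look-back, or she may have used a weaker product.

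**Conclusion.** The gap in the text is certain: allergy is excluded, use is not, and nothing in the available text closes the gap. The direction is also clear if curcumin works, namely dilution toward zero. The size is not established. It rests on an unknown share of users, an SD back-solved from the plan's sample size, a two-sided t-test, and the worst-case assumption that users contribute no contrast. On those terms the loss at 22 per arm is under 2 percentage points of power at 2% users, about 9 at 10%, and about 19 at 20%.

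A reader might take these figures to mean that the trial is underpowered. The documents do not support that, because they give no prevalence of use, and at full retention of 29 per arm even 10% users would leave power above 80%. The table is a sensitivity range. The case for changing the plan is that the gap is real and very cheap to close.

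**What to change.** 1. Add an exclusion for current or recent use of any supplement containing curcumin or turmeric. The investigators should set the look-back. The protocol has two reference points of its own: the 30-day bleeding look-back in the inclusion criteria and the 4 to 6 week washout for oral contraceptives.
2. Add an inclusion criterion: agreement not to take non-study curcumin or turmeric supplements from screening to the end of the 30-day reference period. State explicitly that this includes the wait of up to 30 days between enrollment and first dose.
3. In the medication reviews already scheduled at V1, V2 and V3, ask about such supplements by name and record the answer, so that any use on study can be described and examined in a sensitivity analysis.

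The cost is two criterion lines and one question in an existing review. The planned sample size does not change. The drawback is that a few women who use these supplements would be excluded or would have to wait before entering.

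### The drug-start sentences give no single rule for a woman already past bleeding day 3 at V2, and the start of the 30-day reference period is not stated

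*Combined protocol and SAP*

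**What the plan says.** Four sentences in the protocol govern the start of study drug. Three are in Study design/Clinical Plan.

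1. The "first dose will be taken at the start of enrollment if the subject is on the 3rd day of active bleeding", "or if not bleeding, on day 3 of the next bleeding episode".
2. Drug is not "initiated at the time of enrollment unless they are experiencing bleeding/spotting that day and" on the two preceding days.
3. "Study drug will be started on the 3rd day of an active bleeding" episode.

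The fourth is in Study procedures, Enrollment (V2). The woman will "only start study drug at this visit if they are experiencing an active bleeding episode and this is" "the 3rd day of bleeding/spotting".

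Other text that bears on the point:

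- **Eligibility, Inclusion.** The first route reads "To be eligible, women will need to have >7 days of continuous bleeding/spotting" in the last 30 days. The alternative is two or more episodes in the same 30 days.
- **Enrollment (V2).** Randomization takes place at this visit. The visit may be combined with screening, or scheduled once the infection tests are negative.
- **Study design/Clinical Plan.** A participant with no bleeding episode in the 30 days after enrollment is withdrawn. Total involvement is up to about 60 days, and drug is taken for 30 days.
- **Description of intervention/study drug.** Data collection, apart from side effects and adverse events, lasts 30 days from enrollment. Data on women who are lost are analyzed by intention to treat.

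**The concern.** A woman who is on day 4 or later of a bleed when she attends V2 satisfies the condition in sentence 2, is barred from starting by sentence 4, and falls in neither branch of sentence 1. Staff who work from the clinical plan could start her at the visit. Staff who work from the V2 text would not.

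This matters because she has been randomized by then. If she waits, her treatment moves to a later bleed. If her bleed does not stop, she may never be treated. The start rule also determines how many treated days fall inside the primary outcome window, and the protocol does not say on which day that window opens.

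**Working it through.** No stated figure is in dispute, so the check applies each sentence to a woman on consecutive bleeding day k at V2 and then counts days.

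**Step 1. Start at V2, by bleeding day**

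| k at V2 | Sentence 1 | Sentence 2 | Sentence 3 | Sentence 4 |
|---|---|---|---|---|
| 0 (not bleeding) | wait for day 3 of next episode | no start | wait | no start |
| 1 or 2 | no branch | no start | wait | no start |
| 3 | start | condition met | start | start |
| 4 or later | no branch | condition met | its day has passed | no start |

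The four sentences agree on day 3, and none gives a V2 start before it. From day 4 on they give no common answer.

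**Step 2. What follows for a woman past day 3 if sentence 4 is applied**

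- Her bleed stops and a new one begins: she starts on day 3 of the new one.
- Her bleed continues: there is no next episode, so no start day exists. The withdrawal rule is written for women who have no bleeding episode, so it does not remove her. She is randomized, undosed and still in the trial.

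**Step 3. Timing and the reference period**

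Set V2 = day 0 and let a new episode begin on day d (assumed values). Then first dose = d + 2, last dose = d + 2 + 29 = d + 31, and the days shared by a 30-day window from first dose and one from enrollment (days 0 to 29) = 30 − (d + 2), not below 0.

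| d | First dose | Last dose | Shared days |
|---|---|---|---|
| 5 | 7 | 36 | 23 |
| 10 | 12 | 41 | 18 |
| 20 | 22 | 51 | 8 |
| 30 | 32 | 61 | 0 |

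If the same woman started at V2, her first dose would be day 0 and all 30 days would be shared.

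The 60-day involvement (30 days of waiting + 30 days of drug = 60) implies a window from first dose, and the latest case above, day 61, fits it. Data collection limited to 30 days from enrollment implies a window from enrollment. With the first anchor, a never-dosed woman has no defined window. With the second, her window is defined but untreated, and a late starter has between 23 and 0 treated days in it for the values of d shown.

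**Step 4. Dilution**

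Let p be the share of randomized women who are never dosed, and assume that they have placebo-like outcomes and would otherwise have had the full effect. The planned 6-day difference (Sample size) becomes 6 × (1 − p). Each 10 percentage points of p therefore removes 6 × 0.10 = 0.6 day. The documents do not give p, or the distribution of bleeding day at V2 from which to estimate it.

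**The case against.** The strongest reply is that the sentences do not conflict. Sentence 2 is framed with an unless-clause, which states a necessary condition and does not order a start. The other three all name day 3, and bleeding on a given day and the two before it is an ordinary way to describe day 3. Dosing only on day 3 breaks no sentence. At this single site a coordinator also follows the diaries at least three times a week, partly to check the day of drug initiation.

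Much of this stands. A reader might infer a flat contradiction, and the documents do not support that. What remains is a mismatch in wording plus a case that no sentence covers. Diary monitoring does not fill the gap, since no correct day is defined for this woman.

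Other stronger inferences also go beyond the text:

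- **That she is the typical entrant.** There are two inclusion routes, both look back over 30 days, and neither requires bleeding at V2. She is an expected entrant, and no more can be said.
- **That the heaviest bleeders are lost.** The criteria concern duration and number of episodes, not volume.
- **That first dose is the stated time zero.** It is implied by the 60-day involvement and stated nowhere.
- **That never-dosed women can be set against the allowance of 58 − 44 = 14.** That allowance is for dropout. A woman who is never dosed can still complete her diary, so she is not automatically a lost outcome.

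**Conclusion.** The point holds as an uncovered case with mismatched wording. For a woman past bleeding day 3 at V2, the protocol does not say whether or when she starts. On the strict reading, one whose bleed continues is randomized, never treated and not withdrawn, and she dilutes an intention-to-treat comparison. Separately, the reference period for the primary outcome has no stated start, and the two implied anchors can share as few as 0 of 30 days.

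The effect on the trial result cannot be computed from the documents, because the share of women affected is unknown. The 0.6 day per 10 percentage points is a conversion rate under the stated assumptions, not an estimate. The conclusion itself rests only on the text: the four start sentences, the inclusion route through prolonged bleeding, randomization at V2, and the wording of the withdrawal rule. It is worth correcting because women in this position are to be expected and the correction is cheap.

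**What to change.** The sponsor should:

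1. Reconcile the start sentences in Study design/Clinical Plan and Enrollment (V2), together with the withdrawal rule, into one rule that states what applies to a woman already past day 3 at V2, including one whose bleed does not stop. Which rule that should be is a clinical decision, and this review takes no view on it.
2. Use the same rule in the clinical plan, the V2 text and the study drug handout.
3. State one anchor for the 30-day reference period, and align the data-collection sentence in Description of intervention/study drug with it.
4. Record the bleeding-day number at V2 and at first dose, and report by arm the randomized women who were never dosed.

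Bleeding day at first dose should not be a covariate in the primary comparison. Under a strict day-3 rule it is constant, for never-dosed women it is undefined (so an adjusted model would drop them), and for women who wait it is measured after randomization.

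The cost is protocol wording and one recorded field, which the diary or the visit interview can supply.
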